#### *modified Intent-to-Treat Analysis Set Extended – mITT-Ex*

The mITT-Ex analysis set comprises all subjects in the mITT who complete the first 24 weeks of double-blind treatment (Study Period 1) and receive any amount of the IMP between Week 25 and Week 53 (Study Period 2). The documented failure to take any amount of randomized IMP between Week 25 and Week 53 (Study Period 2) will lead to the exclusion of the subject from the mITT-Ex. The mITT-Ex analysis will be based on the treatment sequence to which subjects were randomized.

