#### **4.3.5 Consequences of Subject Withdrawal or IMP Discontinuation**

Subjects who have been withdrawn from the study or who have discontinued IMP before Week 25 will be considered non-responders for the primary endpoint analysis, except if withdrawal or discontinuation was due to the Ukraine war (see [Section 10.4.2](#)) Withdrawal from IMP during Study Period 1 or Study Period 2 renders a subject ineligible for participation in Study Period 3 of this study.

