## 4.2 Objectives and Endpoints

The primary objective of this study is to assess the efficacy of IgPro20 0.5 g/kg weekly SC doses in comparison to placebo in adult subjects with DM, as measured by responder status based on the TIS assessments at Weeks 17, 21, and 25.

The secondary objectives of the study are:

1. To assess the efficacy, with additional clinical outcome measures, of IgPro20 in comparison to placebo
2. To assess the safety of IgPro20 in comparison to placebo
3. To assess the safety and efficacy of IgPro20 at Week 53
4. To assess the safety of IgPro20 from after completion of Week 53 to the end of study participation

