### 8.2.16 TIS

The TIS is a validated assessment for DM and PM. It is the sum of all available improvement scores (derived from the 6 CSMs) associated with the percent change in each CSM as in [Table 5](#).

According to the [Web calculator for 2016 ACR/EULAR Criteria](#) the TIS calculation requires at minimum CSM1 (Physician Global Disease Activity), CSM3 (MMT-8) and at least 2 other CSMs. Missing CSMs are considered as not changed (improvement score = 0).

---

The TIS calculation will use baseline assessments throughout the study.

CSMs are combined to TIS using the nominal visits. Date of TIS (and possible improvement) is the date of the earliest CSM contributing to the TIS. If some of the core set measures assessed at the Baseline/Week 1 or the Week 25 visit or the Week 53 visit were assessed after start of IMP at the respective visit but within 5 days after start, the core set measures will be considered baseline assessments or included in the TIS calculation for Week 25 or for Week 53, respectively. All these cases will be presented during the BDRM. The same approach will be applied for all other data collected in eCOA data.

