## 10.5 Analysis of Secondary Efficacy Endpoint

All secondary efficacy analyses will be performed for the following periods and analysis sets:

- Week 1-25 by treatment sequence (mITT)
- Week 25-53 by treatment sequence (mITT-Ex)

Raw data and changes from the reference visit will be summarized at all visits as appropriate (Table 11). Comparison between treatment sequences will be performed using statistical models as described below. No imputation is planned for missing data in secondary endpoints. P-values from the statistical models are descriptive.

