**Table 11: Secondary Efficacy Endpoints - Variables**

Endpoint	Variable	Type of summary measure
TIS from Week 5 to Week 53	• TIS values	• continuous
	• Subjects achieving TIS $\geq 20$ points per visit • Subjects achieving TIS $\geq 40$ points per visit • Subjects achieving TIS $\geq 60$ points per visit • Subjects achieving TIS $\geq 20$ points at the end of Study Period 2	• response
	• Time to first achieving TIS $\geq 20$ points • Time to first achieving TIS $\geq 40$ points • Time to first achieving TIS $\geq 60$ points	• time to event
CDASI from Baseline to Week 53	• CDASI total activity score  Note: For Study Period 2 changes from baseline will also be calculated	• continuous
CSMs (except muscle enzymes) from Baseline to Week 53	• Physician Global Disease Activity • Patient Global Activity • MMT-8 • HAQ-DI • Extramuscular global activity	• continuous

Endpoint	Variable	Type of summary measure
	Note: For Study Period 2 changes from baseline will also be calculated	
DOW from Baseline to Week 53	
 
Subjects meeting DOW at least once per period
 
Subjects meeting DOW at least twice per period
 
Subjects meeting DOW more than twice per period
 
	• response
	• Time to meet DOW for the first time	• time to event
	• Subjects meeting DOW followed by oral rescue corticosteroid treatment per period	• response
Oral rescue corticosteroid treatment (from Baseline to Week 25)	
 
Subjects receiving oral rescue corticosteroid treatment
 
Subjects whose oral rescue corticosteroid treatment is tapered
 
	• response
	• Time to first intake of oral rescue corticosteroid treatment	• time to event
EQ-5D-5L from Baseline to Week 53	
 
Mobility
 
Self-care
 
Usual Activities
 
	• cumulative distribution function
Reduction of oral concomitant corticosteroid treatment from Baseline to Week 53	
 
Subjects who start oral concomitant corticosteroid dose taper before Week 25, ie, there is a reduction in week 24
 
Subjects who are able to reduce the oral concomitant corticosteroid treatment at the end of each period by 
 
≥ 25%
 
≥ 50%
 
≥ 75%
 
 
 
	• response

The following additional analyses will be provided:

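### Sequence A's Week 53 response rate is taken on the mITT-Ex, so it is conditional on completing Study Period 1 and omits subjects who stopped IgPro20 earlier

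*SAP*

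**What the plan says.** Secondary objective 3 in SAP 4.2 is "To assess the safety and efficacy of IgPro20 at Week 53". SAP 10.5 runs the secondary efficacy analyses for Weeks 1-25 on the mITT and the later ones as "Week 25-53 by treatment sequence (mITT-Ex". SAP 6 sets the membership rule: "The mITT-Ex analysis set comprises all subjects in the mITT who complete the first 24 weeks of double-blind treatment", and they must also have received some IMP in Study Period 2.

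The response variables in SAP Table 11 include TIS ≥ 20 "points at the end of Study Period 2", TIS ≥ 20/40/60 by visit, and oral corticosteroid reductions of at least 25%, 50% and 75% at the end of each period. TIS keeps the original reference point (SAP 8.2.16: "The TIS calculation will use baseline assessments throughout the study"), so Sequence A's Week 53 TIS is a 52-week IgPro20 outcome.

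SAP 10.5 adds that "Comparison between treatment sequences will be performed using statistical models as described below" and that "P-values from the statistical models are descriptive". It plans no imputation for secondary endpoints and states no non-response rule for them.

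For the primary endpoint, Protocol 4.3.5 takes the opposite approach to the same subjects: "Subjects who have been withdrawn from the study or who have discontinued IMP before Week 25 will be considered non-responders", with an exception for stops due to the Ukraine war. SAP 10.1 says the same in estimand terms.

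**The concern.** A Sequence A subject who stops IgPro20 in Period 1, for instance for lack of efficacy or an adverse event, is a treatment failure at Week 25. At Week 53 the same subject is not in the denominator. Protocol 3.3.1 presents Period 2 as the time when Sequence A can hold or improve its response, so readers will look for durability in this rate. A rate among Period 1 completers overstates how many of those started on IgPro20 are responding a year later.

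The Week 25-53 models also compare groups selected after randomisation. Membership means having stayed 24 weeks on IgPro20 in one sequence and 24 weeks on placebo in the other.

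Two features of the SAP suggest this was not deliberate. Its opening statement in Section 10 names the mITT as the main set for every efficacy endpoint, which does not fit 10.5. For safety, the SAF-IgPro20 set in SAP 6 keeps all treated Sequence A subjects and adds only those Sequence B subjects who entered Period 2. There is no efficacy counterpart.

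**Working it through.** **The plan's own figures.** SAP Table 3 assumes Week 17 response of 0.65 (A) and 0.30 (B). The later conditional probability is 0.90 after response, and 0.20 (A) or 0.10 (B) after non-response. The composite primary responder rate is the probability of response at Week 25 and at Week 17 or 21:

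- A: 0.65×0.9×0.9 + 0.65×0.1×0.2 + 0.35×0.2×0.9 = 0.5265 + 0.013 + 0.063 = 0.6025
- B: 0.30×0.9×0.9 + 0.30×0.1×0.1 + 0.70×0.1×0.9 = 0.243 + 0.003 + 0.063 = 0.309

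Exact enumeration of the one-sided Fisher test at 0.025 with 63 per sequence gives power 0.904, against 0.905 in SAP Table 14. The planning model reproduces.

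**The matching single-visit rate.** The Period 2 variable is TIS ≥ 20 at one time point, so the composite is the wrong yardstick. Under the same assumptions, single-visit response at Week 25 is:

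- A: Week 21 = 0.65×0.9 + 0.35×0.2 = 0.655; Week 25 = 0.655×0.9 + 0.345×0.2 = 0.6585
- B: Week 21 = 0.30×0.9 + 0.70×0.1 = 0.34; Week 25 = 0.34×0.9 + 0.66×0.1 = 0.372

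**The denominator effect.** Let Sequence A have n subjects, s of whom stop IMP in Period 1, and R responders at Week 53, none of them among the stoppers. War-related stops are set aside in both rates. Period 2 stoppers are treated alike in both. Then:

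- rate keeping the stoppers as failures: R/n
- mITT-Ex rate: R/(n-s)
- ratio: n/(n-s) = 1/(1-d), with d = s/n

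The ratio does not depend on R. The documents do not state d, because the power model folds withdrawal into non-response. For assumed d of 5%, 10%, 15% and 20% the factor is 1.05, 1.11, 1.18 and 1.25.

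**In whole subjects.** The SAP gives no Week 53 rate. As an illustration, take n = 63 and R = 41 (65.1%), close to 0.6585×63 = 41.5, with R = 33 (52.4%) as a lower case:

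| Stoppers (d) | mITT-Ex n | R = 41: rate (shift) | R = 33: rate (shift) |
|---|---|---|---|
| 0 (0%) | 63 | 65.1% (0) | 52.4% (0) |
| 3 (4.8%) | 60 | 68.3% (+3.3 points) | 55.0% (+2.6) |
| 6 (9.5%) | 57 | 71.9% (+6.9) | 57.9% (+5.5) |
| 9 (14.3%) | 54 | 75.9% (+10.8) | 61.1% (+8.7) |
| 13 (20.6%) | 50 | 82.0% (+16.9) | 66.0% (+13.6) |

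**Whether another part of the plan restores these subjects.** A combined Period 1 and 2 analysis is planned only for time-to-event variables (SAP 10.5). Subjects who stop IMP in Period 1 are encouraged to stay only to Week 25 (Protocol 4.3.1), so no Week 53 value is planned for them. With no imputation and no non-response rule, moving to the mITT without further wording would leave them missing.

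**The case against.** The strongest reply is that the mITT-Ex suits the question whether those who enter Period 2 keep their response. Objective 3 is not worded as a comparison with placebo, Week 53 lies outside the multiplicity family, and the p-values are descriptive. SAP 9.1 also plans disposition by sequence and period, analysis-set counts and a listing of exclusions, so a reader could rebuild the denominator. All of this stands. It justifies keeping the mITT-Ex tables and limits the harm to a descriptive rate. It does not supply a 52-week rate for those who started IgPro20.

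Four stronger readings are tempting and are not supported.

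- **That the step from the Week 25 primary rate to the Week 53 mITT-Ex rate measures the inflation.** The endpoints differ. Under SAP Table 3, moving from the composite to the single-visit definition raises A from 60.25% to 65.85%, or 5.6 points, with no dropout at all. The by-visit Week 25 TIS ≥ 20 rate has no non-response rule either, so it may already omit stoppers. Nor should the shift be expressed as a share of the planned Week 25 effect: that is a drug-placebo difference, and in Period 2 both sequences receive IgPro20.
- **That all IgPro20 failures leave.** Only Period 1 stoppers, and anyone with no Period 2 dose, leave. Completers with TIS < 20 and rescued subjects who stay on IMP remain. War-related stoppers also leave, and they are not failures under the primary estimand.
- **That it is a 52-week completer rate.** One Period 2 dose is enough for membership, so Period 2 stoppers are in the set.
- **That Sequence B's Period 1 stoppers should be restored in the same way.** They never received IgPro20, and scoring them as IgPro20 non-responders would be wrong.

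**Conclusion.** The point holds as a limited one. Sequence A's Week 53 response rates are conditional on completing Period 1. They exceed a rate that keeps Period 1 stoppers as failures by the factor 1/(1-d): 1.05 to 1.25 for an assumed 5% to 20% stopping, and nothing if no one stops. The direction follows from the set definition. The size rests on d, which the documents do not give, and on counting stoppers as failures, as the primary estimand does apart from war-related stops.

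The Week 25-53 between-sequence models condition on a post-randomisation event and are not randomised comparisons. The primary and key secondary tests use the mITT and are untouched.

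**What to change.** In SAP 10.5, for TIS ≥ 20/40/60 at Week 53 and the corticosteroid-reduction thresholds:

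- Report the Sequence A rate on the mITT, counting non-war withdrawal from IMP or study before Week 53 as non-response. The rule is essential, because changing the set alone does nothing. It also covers Period 2 stoppers, which the factor above does not.
- Show war-related withdrawals excluded and, as a bound, counted as non-responders. The imputation in SAP 10.2 stops at Week 25 and cannot simply be rerun for Week 53.
- Keep the mITT-Ex tables, labelled as subjects who completed Study Period 1, and state that the Week 25-53 between-sequence results are not randomised comparisons. Do not re-enter Sequence B's placebo stoppers as IgPro20 non-responders.
- Reconcile the general statement in SAP 10 with the set assignment in 10.5.

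The cost is SAP wording and a few added tables, with no new data. The downside is a slightly less favourable Week 53 rate.

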#### *Per Protocol Analysis Set - PP*

The PP analysis set comprises all subjects in the mITT without protocol violations. Protocol violations will be defined in detail in the BDRM before unblinding for the primary data analysis (ie, when all subjects have completed all assessments for Study Period 1 and the data has been cleaned for primary data analysis). The PP analysis will be based on the treatment sequence to which subjects were randomized.

#### *Safety Analysis Set - SAF*

The SAF analysis set comprises all subjects who were randomized and received any amount of randomized IMP and will be based on the actual treatment sequence received.

#### *Safety Analysis Set Extended – SAF-Ex*

The SAF-Ex analysis set comprises all subjects in the SAF who complete the first 24 weeks of double-blind treatment (Study Period 1) and receive any amount of the IMP between Week 25 and Week 53 (Study Period 2). The SAF-Ex analysis will be based on the actual treatment sequence received.

*Safety Analysis Set IgPro20 – SAF-IgPro20*

The SAF-IgPro20 analysis set comprises all subjects in the SAF who are randomized to Sequence A, and all subjects in SAF-Ex who are randomized to Sequence B.

*Pharmacokinetic Analysis Set - PK*

The PK analysis set comprises all subjects, without any protocol violations that may impact PK analysis, who provide rich PK samples (Week 37) for non-compartmental PK parameter estimation. Protocol violations that may impact PK analysis will be defined in detail in the BDRM before database lock.

*Safety Analysis Set for Study Period 3 – SAF-P3*

The SAF-P3 Analysis Set comprises all subjects in the SAF-Ex who completed the first 52 weeks of treatment in Study Period 1 and Study Period 2 and received any amount of the IMP after Week 52 (ie, in Study Period 3).

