#### *Safety Analysis Set – SAF*

The SAF analysis set comprises all subjects who are randomized and receive any amount of randomized IMP. The safety analysis will be based on the actual treatment sequence received.

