## 11 Safety Analyses

All Safety analyses will be performed for the following periods and analysis sets:

- Week 1-EOP1 by treatment sequence (SAF)
- Week 25-EOP2 by treatment sequence (SAF-Ex)
- Week 53-EOP3 by treatment sequence (SAF-P3)

Additionally, adverse events will be presented using the following periods and analysis sets:

- IgPro20 Periods (SAF-IgPro20)  
Note: This is restricted to IgPro20 treatment

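### SAF-IgPro20 is built from randomized sequence while SAF and SAF-Ex follow actual treatment, so a Sequence B subject given IgPro20 who stops before Week 25 drops out of the pooled IgPro20 adverse event tables

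*SAP*

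**What the plan says.** Three safety sets are involved, all in SAP Section 6 and Protocol 10.3.

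- **SAF** takes every randomized subject who was dosed. In the SAP it "will be based on the actual treatment sequence received"; the protocol agrees: "The safety analysis will be based on the actual treatment sequence received".
- **SAF-Ex** takes SAF subjects who "complete the first 24 weeks of double-blind treatment (Study Period 1) and receive any amount of the IMP between Week 25 and Week 53". Again, "The SAF-Ex analysis will be based on the actual treatment sequence received".
- **SAF-IgPro20** is built differently. Its first part reads "The SAF-IgPro20 analysis set comprises all subjects in the SAF who are randomized to Sequence A"; its second part adds "all subjects in SAF-Ex who are randomized to Sequence B". The protocol uses the same definition.

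SAP Section 11 gives SAF-IgPro20 one job: an additional adverse event presentation over the IgPro20 periods, with the note "This is restricted to IgPro20 treatment".

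SAP 8.2.8 derives actual treatment from IRT exposure data. It replaces the assigned treatment only where the subject had the wrong product throughout; it gives no rule for a subject who had some of each.

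**The concern.** The purpose of SAF-IgPro20 is to describe adverse events on IgPro20, so membership should follow exposure. It follows allocation instead, while the two sets it draws on are analysed by treatment received. When allocation and exposure differ, a subject exposed to IgPro20 can be left out and a subject never exposed can be left in.

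The omission matters more. A subject who stops early may have stopped because of an adverse event. That event would be shown under IgPro20 in the SAF table and be absent from the pooled IgPro20 table, and deciding what to do about it after unblinding is what the SAP should prevent.

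**Working it through.** The plan states no figure on this point. The check is to apply the definitions to each way in which allocation and exposure can differ. Inputs: set definitions (SAP 6, Protocol 10.3), actual-treatment rule (SAP 8.2.8), the Section 11 note, and the treatment sequences (SAP 4.3: both arms are assigned IgPro20 from Week 25).

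1. **Randomized to B, given IgPro20 throughout Period 1, stopped before Week 25.** The wrong product was received for the whole of treatment, so 8.2.8 reclassifies the subject and SAF reports the events under IgPro20. The subject did not complete 24 weeks, so is not in SAF-Ex and not in SAF-IgPro20. Events and exposure are lost from the pooled set. The Section 11 note cannot help: it narrows what is counted among members and does not add members.
2. **Randomized to A, given only placebo, stopped before Week 25.** The subject is in SAF and was randomized to A, so is in SAF-IgPro20 with no IgPro20 exposure. If the note means treatment actually received, the events drop out, but the subject can still count in the percentage denominator. If it means assigned treatment, placebo events enter the pool.
3. **Randomized to B, given IgPro20 in Period 1, continued into Period 2.** Correctly a member. The Period 1 events count only if the note means treatment actually received.
4. **Randomized to A, given placebo in Period 1, continued on IgPro20 in Period 2.** Correctly a member. The Period 1 placebo events stay out only if the note means treatment actually received.
5. **Given the wrong product for part of Period 1 only.** SAP 8.2.8 does not reclassify the subject, so SAF and SAF-IgPro20 do not disagree through this wording. However, a Sequence B subject with some IgPro20 who stops before Week 25 is still absent from the pooled set.

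Membership is therefore wrong in case 1, in case 2 and in the last part of case 5. In cases 3 and 4 membership is right and only the meaning of the note is open.

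**Scale.** Planned randomization is 126 subjects, 63 per sequence.

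- Share of planned subjects per case: 1/126 = 0.8%.
- Share of exposure: assume that everyone completes Periods 1 and 2, and leave Period 3 out. IgPro20 time is 63 × 52 + 63 × 28 = 3,276 + 1,764 = 5,040 subject-weeks. A subject stopping before Week 25 contributes at most 24 weeks: 24/5,040 = 0.5%. Dropout would raise this share; Period 3 time would lower it.

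**The case against.** The strongest reply is that this is a corner case with safeguards around it.

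- **Supply is controlled.** IMP is assigned centrally by IRT, and the documents report no dispensing error. This stands: with no error the effect is zero.
- **SAP 8.2.8 is narrow.** From Week 25 both sequences are assigned IgPro20, so a subject given the wrong product only in Period 1 who then enters Period 2 did not have the wrong product throughout. Read literally, SAF and SAF-IgPro20 part company only for a subject who had the wrong product at every dispensing and stopped before Week 25. This stands, and it rules out the reading that any mis-dispensed subject distorts the pool.
- **The Section 11 note is a second filter.** On its natural reading it removes placebo-time events, and SAP 8.2.24 points the same way by setting the dose to zero when actual treatment is placebo. This largely answers the worry that placebo events enter the pool. It does not settle the denominator in case 2 and does nothing for case 1.
- **Details may sit elsewhere.** SAP 8.2 says that separate dataset specifications hold the full derivations, so the programming may already use exposure. That is possible, but it would then depart from the set definition in both documents.

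A reader might also infer that the thromboembolic stopping rule is affected. The documents do not support that. The relative risk in SAP 11.3 counts events and observation time under the treatment given and does not refer to SAF-IgPro20. Thromboembolic events reach this set only descriptively, through the special-interest lines of the overview and the virtual system organ class in SAP 11.2.

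Nor is failure to match the SAF tables a fault in itself. Those cover Period 1 by sequence, while the pooled presentation covers IgPro20 periods across sequences; they differ by design.

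**Conclusion.** The inconsistency is real and stands in both documents. As written, the membership rule wrongly omits a Sequence B subject who received IgPro20 in Period 1 and stopped before Week 25, and wrongly keeps a Sequence A subject who never received it. Whether placebo-time events are excluded rests on an unstated meaning of the Section 11 note.

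The size is small: zero without mis-dispensing, otherwise at most about 0.8% of planned subjects, or about 0.5% of IgPro20 time under full completion, per case. Only the additional descriptive adverse event presentation is affected.

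It would be too strong to say that every Sequence A subject who received placebo is wrongly counted as exposed: one who reaches Period 2 and is dosed with IgPro20 belongs in the set. This is a wording correction worth making because it is free, not a threat to the trial's safety conclusions.

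**What to change.** 1. In Protocol 10.3 and SAP Section 6, define SAF-IgPro20 as all SAF subjects who actually received any IgPro20. Judge receipt from the exposure data, not from the whole-of-treatment rule in SAP 8.2.8; otherwise a partly mis-dispensed subject would still be classed as assigned.
2. In the same definition, count events and time at risk from the first actual IgPro20 infusion, and only while on IgPro20.
3. In SAP Section 11, state that the restriction to IgPro20 treatment means treatment actually received.

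The cost is about a sentence in each of these places. Nothing changes in the results if no dispensing error occurred, and no other analysis set, test or sample size figure is touched. The change should be made before unblinding for the primary data analysis.
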